#### **4.4 Secondary Subjects**

N/A

#### **4.5 Number of Subjects**

##### **A. Total Number of Subjects**

20

##### **B. Total Number of Subjects If Multicenter Study**

N/A

##### **C. Require Number of Subjects to Complete Research**

40

##### **D. Feasibility of Recruiting**

We anticipate approximately half of the patients approached will consent to this trial.

#### **4.6 Consent Procedures**

##### **A. Consent**

- **Documenting Consent**

Adult consent form provided.

- **Waiver of Documentation Of Consent**

N/A

- **Waiver or Alteration of Consent Process**

- (i) **Waiver or Alteration Details**

N/A

- (ii) **Destruction of Identifiers**

N/A

- (iii) **Use of Deception/Concealment**

N/A

##### **B. Consent Process**

- **Location of Consent Process**

Version Number: 5

Protocol Number: Pro2018001008

PI Name: [name]

Protocol Title: TENS after Cesarean Delivery

10

RESERVED FOR IRB STAMP

DO NOT MODIFY THIS SPACE

IRB ID: Pro2018001008

IRB Form Version: 01/2018 Approval Date: 7/19/2022

Expiration Date: 7/18/2023

Prenatal patients at the Rutgers Medical Group Obstetrics and Gynecology or Maternal Fetal Medicine practices, or the High Risk Obstetric Perinatal Clinic will be approached for study inclusion. Consent will occur in these locations.

■ **Ongoing Consent**

Consent will be reconfirmed following delivery prior to application of the device.

■ **Individual Roles for Researchers Involved in Consent**

[name] or [name] will obtain informed consent. [name], [name] or [name] will reconfirm consent at the time of device application.

**1. Consent Discussion Duration**

20-30 minutes

**2. Coercion or Undue Influence**

The patient will be reassured that non-inclusion in the study will result in routine standard of care

**3. Subject Understanding**

The device will be available at the time of consent to trial prior to cesarean, in order to ensure patients have good expectations of their postpartum course.

#### 4.7 Special Consent/Populations

**A. Minors-Subjects Who Are Not yet Adults**

■ **Criteria for Consent of Minors**

Patients under the age of 18 will not be permitted to participate in this study. We will verify with inpatient medical records to confirm that participant is over the age of 18.

■ **Wards of the State**

**1. Research in NJ Involving Minors**

N/A

**2. Research Outside of NJ Involving Minors**

N/A

■ **Parental Permission**

N/A

■ **Non-Parental Permission**

N/A

■ **Assent Process**

N/A

**1. Documentation of Assent**

N/A

■ **Non-English Speaking Subjects**

None, only English-speaking subjects are eligible for this study.

**1. Process for Non-English Speaking Subjects**

N/A

■ **Short Form Consent for Non-English Speakers**

N/A

**B. Adults Unable to Consent / Cognitively Impaired Adults (for interventional studies)**

■ **NJ Law-Assessment of Regaining the Capacity To Consent**

If the attending clinician caring for the patient considers her able to consent for cesarean surgery, this will be considered sufficient for capacity to consent for this research trial.

■ **Capacity To Consent**

Surrogate consent will not be sought.

■ **NJ Law-Selecting A Witness**

Nursing or medical staff in the prenatal office may serve as a witness to consent if necessary.

■ **Removing a Subject**

If a patient withdraws consent at the time of cesarean or at any time of device application, no outcome data will be collected, and all study documents including consent and log of TENS

device will be destroyed by shredding. If a subject requests removal after data collection, data will be destroyed.

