### **1.3 Research Design and Methods**

**OVERVIEW.** This study is a pilot randomized interventional trial. Two categories of participants will be randomly assigned to an invention or control group, using a random number generator: normal cesarean without associated comorbidity, or cesarean in women with a history of opioid addiction, as defined by use of opioid replacement medications of either methadone or Subutex during pregnancy. The control group will receive usual care which is

Version Number: 5

Protocol Number: Pro2018001008

PI Name: [name]

Protocol Title: TENS after Cesarean Delivery

4

RESERVED FOR IRB STAMP

DO NOT MODIFY THIS SPACE

IRB ID: Pro2018001008

[figure not shown]
IRB Form Version: 01/2018 Approval Date: 7/19/2022

Expiration Date: 7/18/2023

standard post-operative pain management with opioids and NSAIDS. The intervention group will receive usual care plus TENS therapy beginning 8 hours after C-section and continuing to discharge. Both groups will receive medications for pain as requested or ordered by the doctor.

**RESEARCH PROCEDURES.** Patients will be identified for participation in several locations. Prenatal patients at the Rutgers Medical Group Obstetrics and Gynecology or Maternal Fetal Medicine practices, or the High Risk Obstetric Perinatal Clinic will be approached for study inclusion. Physicians that have a direct treatment relationship with the patient will inform the patient about the study and invite them to enroll. Consent for participation will be reviewed with the principal investigator and signed prior to delivery hospitalization. Randomization will follow consent, and patients randomized to intervention will have teaching performed about how to use the device at the time of consent.

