**DURATION OF STUDY.** Study duration will be no more than 12 weeks. This will include up to 6 weeks prior to delivery for study approach and consent, delivery hospitalization, and 6 weeks postpartum for pain assessments at postpartum visits. There will be no long-term follow up.

**PRIMARY and SECONDARY ENDPOINTS.** Primary endpoint of this pilot study is a total of 10 normal patients undergoing cesarean, and 10 patients with history of opioid addiction. Intervention will be performed in 5 patients in each group. Safety data will be reviewed following the first 10 patients to evaluate for worsening patient scores relative to controls.

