##### **▪ Timing and Frequency**

Survey will be performed at hospital discharge, as well as at 6 weeks postpartum.

Version Number: 5

Protocol Number: Pro2018001008

PI Name: [name]

Protocol Title: TENS after Cesarean Delivery

7

RESERVED FOR IRB STAMP

DO NOT MODIFY THIS SPACE

IRB ID: Pro2018001008

IRB Form Version: 01/2018

7/19/2022

Approval Date:

7/18/2023

Expiration Date:

7/18/2023

▪ **Location**

Surveys will be supplied to patient at bedside at discharge, and in the outpatient office during routine postpartum visit. However, if patients do not present for their routine 6 week postpartum visit, the final survey will be mailed to their last address of record, with a self-addressed stamped envelope to facilitate completion of study activities.

[figure not shown]
▪ **Procedures for Audio and Visual Recording**

N/A

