#### **4.3 Subject Randomization**

A random number generator will be used for randomization, with even groups randomized to no intervention, and odd groups to intervention.

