### **D. Frequency of Data Collection**

After each pair of intervention/control

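### Section 4.7 shreds the records of women who withdraw consent after randomisation, and no available text keeps a count by arm, in a pilot meant to assess acceptability

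*Protocol*

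**What the plan says.** Order of events. Protocol section 1.3 places allocation at the prenatal stage: "Randomization will follow consent, and patients randomized to intervention will have teaching performed about how to use the device at the time of consent". Section 4.6 B adds a second consent point: "Consent will be reconfirmed following delivery prior to application of the device".

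Withdrawal. Section 4.7 B, under Removing a Subject, states: "If a patient withdraws consent at the time of cesarean or at any time of device application, no outcome data will be collected". It adds that the study paperwork, with the consent form and the device log among it, is shredded. It then says: "If a subject requests removal after data collection, data will be destroyed". The rule sits under a form heading for adults unable to consent, but it is worded for any patient, and the available text contains no other withdrawal rule.

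Acceptability. Section 1.5 gives acceptability as one purpose of the pilot, and section 1.9 B includes questions on it in the questionnaire. On timing, section 1.9 A says: "Survey will be performed at hospital discharge, as well as at 6 weeks postpartum".

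Records of allocation. Section 4.3 describes the method: "A random number generator will be used for randomization, with even groups randomized to no intervention, and odd groups to intervention". Section 6.3 D sets safety data collection: "After each pair of intervention/control". Neither mentions a retained list or a count of withdrawals. The SAP names no acceptability outcome or denominator. Its missing-data paragraph deals with values absent at some time points, not with women whose whole record is gone.

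**The concern.** A woman who withdraws at cesarean or at the device step has already been randomised. If section 4.7 is followed as written, her data are not collected, her paperwork is destroyed, and nothing in the available text requires even her number to be kept.

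This matters most for acceptability. A woman who withdraws because she does not want the device is direct evidence on that question, yet only women still in the study can answer the survey. If acceptability is summarised among respondents, it describes those who stayed. Without counts by arm and stage, a reader cannot tell whether that differs from the picture among all women assigned to TENS. The pilot is also meant to support larger trials, whose planners will need refusal and withdrawal counts by arm.

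**Working it through.** **Inputs.** For the TENS arm, section 1.3 says: "Intervention will be performed in 5 patients in each group". There are two groups, so 2 × 5 = 10 TENS women. Section 1.5 gives four cells of five: 4 × 5 = 20, which reproduces the stated total. The documents give no withdrawal rate and do not say whether withdrawn women are replaced. Every withdrawal count below is therefore an assumption.

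**Acceptability, no replacement.** Let w be the TENS women who withdraw, s the stayers who accept, and k the withdrawers who would have accepted. The error of the respondent figure is

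s/(10 − w) − (s + k)/10.

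*(a) All withdrawals are prompted by the device (k = 0) and all stayers accept (s = 10 − w).* The error is 1 − (10 − w)/10 = w/10. Limits are exact (Clopper-Pearson) 95% lower limits.

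| w | Respondents (lower limit) | All randomised to TENS (lower limit) | Error, points |
|---|---|---|---|
| 1 | 9/9 = 100% (66.4%) | 9/10 = 90% (55.5%) | +10 |
| 2 | 8/8 = 100% (63.1%) | 8/10 = 80% (44.4%) | +20 |
| 3 | 7/7 = 100% (59.0%) | 7/10 = 70% (34.8%) | +30 |

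*(b) As (a), but women are replaced until 10 complete.* The error is 1 − 10/(10 + w). Respondents always show 10/10, against 10/11 = 90.9%, 10/12 = 83.3% and 10/13 = 76.9%: +9.1, +16.7 and +23.1 points.

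*(c) Withdrawals are unrelated to the device, the withdrawers would have accepted (k = w), there is no replacement, and 8 of 10 would accept overall.* Respondents show 7/9 = 77.8%, 6/8 = 75.0% and 5/7 = 71.4%, against 8/10 = 80%: −2.2, −5.0 and −8.6 points. In this case, counting withdrawals as non-acceptance would give 7/10, 6/10 and 5/10, which is 10, 20 and 30 points too low. Such a figure can serve only as a worst case.

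**Chance that it arises.** The probability that at least one of 10 TENS women withdraws is 1 − (1 − p)^10. For assumed p of 5%, 10% and 20% this is 40%, 65% and 89%.

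**Pain.** This used 100,000 simulated arms of 10 standard-normal scores, dropping the 1, 2 or 3 women highest on a variable correlated r with pain, with a full control arm of 10. The standard error of the arm difference in SD units is √(1/10 + 1/(10 − w)) = 0.459, 0.474 and 0.493.

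| r | Shift in TENS mean, w = 1 / 2 / 3 (SD) |
|---|---|
| 0.5 | −0.084 / −0.157 / −0.227 |
| 0.3 | −0.052 / −0.095 / −0.137 |
| 0 | about 0 |
| −0.3 | +0.051 / +0.096 / +0.138 |
| −0.5 | +0.086 / +0.159 / +0.228 |

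Relative to the standard error, the shift runs from about 0 at r = 0 to 0.228/0.493 = 0.46. It uses one score per woman, so it indicates only the order of size for the SAP's repeated-measures analysis.

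**The case against.** Several objections have force.

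- **Stopping the device is not leaving the study.** Section 4.7 acts only on withdrawal of consent or requested removal. Section 1.3 lets a woman take the device off when she wishes and provides an on/off record. Section 1.9 B asks about intended and actual use. Limited use by women who stay is therefore captured. What stands is narrower: section 4.7 does not say that a woman who declines the device at reconfirmation remains in follow-up.
- **A count may be recoverable.** A reader might infer that withdrawn women vanish altogether. The documents do not support that. Section 4.7 does not say that the randomisation sequence or the pair tracking in section 6.3 is destroyed, and randomised minus analysed by arm could show these women as a number. What stands is that no such count is described.
- **Unequal loss between arms.** Because only TENS women reach the device step, a reader might infer that this arm loses more. The documents give no withdrawal figures, and withdrawal at cesarean can happen in either arm.
- **Text that could not be checked.** The consent pages were unavailable, as were protocol pages around the schedule of events, staff and site sections. The absence of a count is a statement about the available text only.
- **The size depends on assumptions.** Case (a) needs every withdrawer to reject the device and every stayer to accept it, and the SAP plans no such percentage. Section 4.5 C also gives 40 subjects. That may mean women approached, since 20/0.5 = 40 at the 50% consent rate in section 4.5 D. If it were the sample, there would be 20 TENS women and the maximum would be 5 points per withdrawal.
- **Erasure protects privacy.** Cells hold five women, and section 4.9 D treats narcotic use as sensitive. This supports honouring every request for destruction. It does not require automatic shredding without asking, and it does not rule out a tally without identifiers.

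**Conclusion.** The point holds in a limited form and should be corrected. As written, section 4.7 discards the records of women who withdraw consent after randomisation, and no available passage provides a count by arm. Device-prompted withdrawals would then be missing from acceptability among respondents.

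With 10 TENS women, the overstatement is at most about 10 points per withdrawal if all withdrawals are prompted by the device and all stayers accept. It is somewhat less if women are replaced, and the error can reverse if they leave for unrelated reasons. The exact intervals overlap widely, so this is a distortion of reporting, not a demonstrable difference. The pain comparison adds little to the concern: 0 to about 0.5 standard errors, sign unknown. Confidence is medium, because all withdrawal counts are assumed and some pages could not be checked.

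**What to change.** In section 4.7 and the consent form:

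1. State that declining or stopping the device is not by itself withdrawal of consent, and that such women stay in follow-up and are analysed in their assigned arm.
2. Replace automatic shredding with a question at withdrawal: may data already collected be kept? Honour any request for destruction.
3. Keep a de-identified tally of women randomised, withdrawn and analysed, by arm and stage (at cesarean, at device application, later). It should hold no name, study ID or date, a reason only if volunteered, and opioid-history group only where cell sizes do not identify anyone.

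In the SAP, report the tally beside acceptability among respondents. Add a figure over all women randomised to TENS that counts withdrawals as non-acceptance, labelled as a worst case.

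The SAP is dated 2024 and is partly in the past tense, so enrolment may be over. If so, report the flow by arm from whatever randomisation records survive and state the limitation.

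Cost: one clarifying sentence, one question at withdrawal, one tally sheet and one flow table, with no extra visits or staff. The downside is slightly less complete erasure in a small population whose opioid data are sensitive.

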#### **4.8 Economic Burden and/or Compensation for Subjects**

##### **A. Expenses**

None

##### **B. Compensation/Incentives**

Subjects will be provided with a \$25 gift card for study participation at the conclusion of all study procedures, during the 6 week postpartum visit. If the subject fails to present for the 6 week visit, the gift card will be mailed to the subject along with the final survey, as well as a signature form confirming receipt of gift card for regulatory confirmation. This will be sent via certified mail to confirm receipt.

##### **C. Compensation Documentation**

Gift card distribution will be signed by the patient and kept in a log with the patient's consent.

#### **4.9 Risks to Subjects**

##### **A. Description of Subject Risk**

Research has shown that TENS therapy is a safe device when used appropriately after surgery. Minor tingling is normal during TENS therapy. However, some patients find the tingling sensation from the device to be uncomfortable when the intensity of the device is too high. If this occurs, the intensity may be turned down. In rare cases, patients have developed adverse skin irritation or rash at the sites where the electrodes are placed. There are no anticipated long-term complications to cesarean scar wound healing.

There is also the risk of loss of privacy. However, data will be associated with a subject study ID number, and protected health information will not be recorded.

##### **B. Procedures for Risks to Embryo, Fetus, and/or Pregnant Subjects**

None, as all interventional study procedures will be conducted postpartum.

##### **C. Risks to Non-Subjects**

None

##### **D. Assessment of Social Behavior Considerations**

Postoperative pain is a common cause of stress, especially in the postpartum period. In other pilot studies, this device has demonstrated good acceptability among patients. However, it is possible that a new mother may feel overwhelmed by the addition of a device for pain management.

###### **▪ Reasonably Foreseeable Risks**

This risk is overall low. Device use is unlikely to increase potential for postpartum stress or mood disorders.

###### **▪ Risk Of Imposing An Intervention On Subject With Existing Condition**

Patients with known history of cardiac arrhythmia or pacemaker will be excluded. However, the subject will be instructed to stop use of the device and call the study staff if palpitations occur.

###### **▪ Other Foreseeable Risks**

None

###### **▪ Observation And Sensitive Information**

Use of postoperative narcotic pain medication is highly individual in the inpatient setting, and may be considered sensitive. However, in data collection, PHI will not be associated with any documentation of study outcome measures, including drug related information.

##### **E. Minimizing Risks**

The patient will be taught about methods to reduce skin and muscle tingling at the time of device application. The lowest effective setting will be used. She will be assessed for palpitations when the device is turned on.

##### **F. Certificate of Confidentiality**

N/A

#### **G. Potential Benefits to Subjects**

Potential for decreased postoperative pain and decreased narcotic use.

#### **H. Provisions to Protect the Privacy Interests of Subjects**

No protected personal health information will be recorded. Surveys and data collected will be labeled only with subject study ID. Consent forms will be the only source of PHI, which will be kept locked in the research coordinators office.

#### **I. Research Team Access to Subject Data**

Data will be collected from the Sunrise Clinical Manager inpatient record. It will be directly imputed into an Excel spreadsheet, without use of identifiers.

### **4.10 Secondary Data – Records/Chart Reviews/Databases/Tissue Banks/etc.**

N/A

### **4.11 Chart/Record Review Selection**

Data will be collected by [name]. It will be collected at the time of discharge survey conduct on the RWJUH postpartum floor. Items collected from the patient's flowsheets will include pain ratings and subjective incisional complaints, number and type of pain medications used, patient satisfaction with pain control, time to first bowel movement, level of sedation and time to OOB. This will be directly imputed into an Excel spreadsheet on the investigator's password protected laptop provided by the Rutgers IT department, without identifiers.

### **4.12 Secondary Specimen Collection**

N/A

## **5.0 Special Considerations**

### **5.1 Health Insurance Portability and Accountability Act (HIPAA)**

N/A

### **5.2 Family Educational Rights and Privacy Act (FERPA)**

N/A

### **5.3 NJ Access to Medical Research Act**

N/A

### **5.4 Code of Federal Regulations Title 45 Part 46 (Vulnerable Populations)**

#### **A. "Special" Classes Of Subjects**

No special classes will be included, as all interventional study procedures will be conducted postpartum.

## **6.0 Research Data Protection and Reporting**

### **6.1 Data Management and Confidentiality**

- A. Primary outcome measures of daily median pain scores will be compared using nonparametric statistical methods. Survey responses will also be compared using Chi-square for proportions, and non-parametric methods for ordinal data.
- B. Power analysis is not performed as this is a pilot study.
- C. No PHI will be recorded in any datasheet. Data sheets will be maintained in a password protected file on the password protected principle investigators' laptop.
- D. Because all data will be collected at the time of subject discharge, data should be complete and clean for each individual at the time of collection.

Version Number: 5

Protocol Number: Pro2018001008

PI Name: [name]

Protocol Title: TENS after Cesarean Delivery

13

RESERVED FOR IRB STAMP

DO NOT MODIFY THIS SPACE

IRB ID: Pro2018001008

Approval Date: 7/19/2022

Expiration Date: 7/18/2023

**E.** Data will be shared through University secure email among study investigators only. Source data will be destroyed following data analysis, anticipated to be 1 year after completion of study procedures.

## **6.2 Data Security**

No PHI will be recorded in any datasheet. Data sheets will be maintained in a password protected file on the password protected principal investigators' laptop. Laptop will be provided by the Rutgers IT department.

## **6.3 Data and Safety Monitoring**

### **A. Periodic Data Evaluation**

Data will be evaluated after pairs of intervention and control subjects are enrolled to compare differences. If 3 consecutive sets of intervention/controls demonstrate worse outcomes for intervention subjects, the study will be suspended. Additionally, interim data analysis will be performed by the project statistician after enrollment of 50% of subjects to ensure that device usage does not cause increased pain.

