### **1.5 Sample Size Justification**

This is a pilot feasibility study to evaluate effectiveness and acceptability in our patient population of TENS use throughout delivery hospitalization. We aim to have 20 participants total: 5 in control and 5 in intervention without history of opioid addiction, and 5 in control and 5 in intervention with history of opioid addiction/misuse. This sample size is comparable to other shorter term pilot studies. This pilot study will serve as the basis for larger trials in the future, with larger sample size powered to demonstrate reduction in pain scores. We anticipate recruitment for this trial will take approximately 6-9 months.

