#### **D. Subject Screening**

- Physicians that have a direct treatment relationship with the patient will inform the patient about the study and invite them to enroll. [name] will confirm eligibility thereafter.

- **Inclusion Criteria**

- Women aged between 18 and 45 years
- Understand and be able to follow written and oral instructions in English
- Provide written informed consent
- History of prior opioid addiction for half of the patients. (Opioid use will be obstetric patients on narcotic replacement with methadone or subutex.)

- **Exclusion Criteria**

History of cardiac arrhythmia or pacemaker usage

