### **G. Tests for Safety Data**

Non-parametric analysis of median daily pain score.

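### The 50% interim is said to ensure that TENS does not increase pain, but a rank test on about 5 v 5 women would miss a 1 SD increase roughly 60 to 79% of the time

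*Protocol*

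**What the plan says.** Protocol 6.3.A describes two layers of monitoring. Outcomes are compared after each intervention/control pair, and three consecutive sets that are worse for TENS suspend the study. In addition, the project statistician performs an interim analysis "after enrollment of 50% of subjects to ensure that device usage does not cause increased pain".

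Section 6.3.G gives the safety method in one line: "Non-parametric analysis of median daily pain score". Section 1.3 describes what appears to be the same look in milder terms: "Safety data will be reviewed following the first 10 patients to evaluate for worsening patient scores relative to controls".

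On size, section 1.5 states "We aim to have 20 participants total: 5 in control and 5 in intervention without history of opioid addiction", with the same numbers for women with such a history, and section 4.5.A also gives 20. Section 4.5.C, under "Require Number of Subjects to Complete Research", gives 40. Section 6.1.B adds: "Power analysis is not performed as this is a pilot study". The SAP does not mention the interim.

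**The concern.** The protocol gives the interim a purpose, to ensure that pain is not increased, which an analysis of about ten women can hardly serve. With so few women, the absence of a significant difference is the likely result even when the device does appreciable harm. If it were taken as assurance, the second half of enrolment would proceed in the belief that increased pain had been excluded.

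The first ten women are also counted without regard to opioid history. Half of the trial is meant to be women on methadone or Subutex, yet nothing requires any particular number of them to be in the look. A reassuring pooled result could rest on very few of them.

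**Working it through.** **Inputs from the documents**
- Planned total 20 (Protocol 1.3, 1.5, 4.5.A). 50% × 20 = 10, which agrees with the first 10 patients in section 1.3.
- Allocation by odd or even random number (section 4.3), with no blocking described. About 5 v 5 is expected but not guaranteed.
- Method: non-parametric, not named (section 6.3.G).
- No power, level, sidedness or detectable harm is stated for the interim, so there is no plan figure to reproduce.

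**Assumptions:** exact Mann-Whitney test, 5% level shown one- and two-sided, one normally distributed pain summary per woman, equal SD in the arms, harm expressed as a shift in SD units.

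**Step 1. Rejection regions at 5 v 5.** There are C(10,5) = 252 equally likely rank arrangements under no effect. Let U count the TENS/control comparisons in which the TENS score is lower, so that small U points to harm. The numbers of arrangements with U = 0, 1, 2, 3, 4 are 1, 1, 2, 3, 5.
- One-sided 5%: reject for U ≤ 4, probability 12/252 = 0.0476.
- Two-sided 5%: reject for U ≤ 2 in the harm direction, probability 4/252 = 0.0159, or 0.032 over both tails.

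**Step 2. Miss rates at 5 v 5** (simulation, 200,000 samples per shift):

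| Increase in pain | Missed, one-sided 5% | Missed, two-sided 5% |
|---|---|---|
| 0.5 SD | 83% | 93% |
| 1.0 SD | 60% | 79% |
| 1.5 SD | about 33% | 57% |
| 2.0 SD | 13% | 32% |

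**Step 3. Departures from 5 v 5, at 1 SD**
- An exact 5/5 split of ten women under simple randomisation has probability C(10,5)/2^10 = 252/1024 = 0.246. Averaged over all splits, the miss rate is about 68% (one-sided) and 80% (two-sided).
- Consent may come up to 6 weeks before delivery, and pain data are collected at discharge, so ten women enrolled may mean fewer than ten outcomes. At 4 v 4, detection falls to about 24% (one-sided) or 14% (two-sided). At 3 v 3 the smallest two-sided p is 2/C(6,3) = 2/20 = 0.10, so 5% cannot be reached.
- If the total were 40, a 10 v 10 look would miss 35% (one-sided) or 49% (two-sided).

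**Step 4. What an interval would show.** The 95% half-width for a difference in means at 5 v 5 is t(0.975; 8 df) × √(1/5 + 1/5) × SD = 2.306 × 0.632 × SD = 1.46 SD, or about 1.5 SD.

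**Step 5. The three-pair rule.** Assume independent pairs and no ties. The chance that a pair is worse for TENS is p = Φ(δ/√2), where δ is the harm in SD. Within five pairs, the chance of three consecutive worse pairs is p³(3 − 2p).
- No effect: p = 0.50, giving 0.125 × 2 = 0.25. By ten pairs it is 0.51.
- 1 SD harm: p = 0.76, giving 0.439 × 1.48 = 0.65. By ten pairs it is about 0.92.

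**The case against.** **The plan contains no rule by which a non-significant result clears the device.** This is right. Apart from the verb in 6.3.A, nothing says so, and section 1.3 describes the look modestly. The test, the 5% level, normality and the 1 SD harm are all supplied here because the plan gives none. What remains is a stated purpose that the analysis cannot meet.

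**This is a pilot, and the lack of a power analysis is disclosed.** Also right. The point asks for no larger sample. Waiving a power calculation does not support a claim of assurance.

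**The pair rule is the main protection.** A reader might infer that the monitoring as a whole misses a 1 SD harm 60 to 79% of the time. It does not: those rates describe the interim alone. The pair rule would trigger in about 65% of trials by five pairs and 92% by ten under such a harm. It would also trigger in 25% and 51% with no effect, so it is unspecific, and it leaves the claim made for the interim unsupported.

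**Opioid-history women.** A reader might infer that the interim is incapable of flagging harm in this category. It is true that five women split 3 v 2 cannot give p below 1/C(5,2) = 0.10 one-sided, but no within-category interim test is planned, so this is no fault in the plan. A reader might also want the look held until five women per category are discharged. In simulation, with at most ten per category, that moves it to a median of 12, 14 or 15 of 20 women if opioid-history women join at the same, half or a quarter of the other category's rate. Those rates are assumptions. A half-way look would become a much later one, for by-category intervals too wide to use.

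**Conclusion.** The concern holds as a mismatch between the purpose stated in 6.3.A and what about ten women can show. At 5 v 5, an exact rank test at 5% would miss a 1 SD increase in pain about 60% of the time (one-sided) to 79% (two-sided), and a 1.5 SD increase about 33% to 57%. A non-significant interim cannot be read as ruling out increased pain.

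The size depends on the assumed test, level and normality, and on a total of 20. Sections 1.3, 1.5 and 4.5.A support 20; the 40 in section 4.5.C must be reconciled with it. With 40 the problem shrinks to a one-sided miss rate of about 35% at 1 SD but does not vanish. The documents do not support the wider inference that harm would go unnoticed, because the pair reviews run alongside.

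**What to change.** - **6.3.A:** state the purpose as looking for a large increase in pain, in place of ensuring that there is none. Give the detection rates above with their assumptions.
- **6.3.G:** report the pooled TENS minus control difference in the protocol's own median daily pain score, with its confidence interval, read against a margin that the sponsor fixes beforehand. Do not rely on the non-parametric test alone. Say how a woman's daily values are combined. At 5 v 5 the 95% half-width is about 1.5 SD, so the interval will be wide; its merit is that it shows what has not been excluded.
- **1.3 and 6.3.A:** keep the look at the first 10 women, counted when their discharge pain data are available. List how many come from each opioid-history category, so that no reassurance is claimed for one with few women. Do not delay the look to fill a category.
- **4.5:** reconcile 20 with 40.

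The cost is a few sentences of protocol text, slightly more analysis, a short wait for the tenth discharge, and a less reassuring statement of what the interim shows. The pair reviews continue unchanged.
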